#### **Study duration**

Each subject will spend a total of approximately 13.5-20 hours of participation in the study over 11 study sessions. The study schedule is as follows: Visit 1: Consent/Screening (1-3 hours) Visit 2: Baseline MRI (1.5-2 hours) Visit 3: TMS/fMRI (2-2.5 hours) Visit 4-6: 1st Neuromodulation Session (1-1.5 hours each) Visit 7: TMS/fMRI (1.5-2 hours) Visit 8-10: 2nd Neuromodulation Session (1-1.5 hours each) Visit 11: TMS/fMRI (1.5-2 hours).

#### **Resources necessary for human research protection**

Describe research staff and justify that the staff are adequate in number and qualifications to conduct the research. Describe how you will ensure that all staff assisting with the research are adequately informed about the protocol and their research related duties. Please allow adequate time for the researchers to conduct and complete the research. Please confirm that there are adequate facilities for the research.

Staff will be trained on the protocol and inclusion/exclusion criteria. TMS protocols will involve direct training with the Principal Investigator and the study physician, [name]. Facilities will include Penn laboratory spaces specializing in advanced computing and analysis of neuroimaging and cognitive datasets. Scans will be conducted on a Siemens Prisma 3 Tesla whole-body MRI, housed in the Center for Advanced Magnetic Resonance Imaging and Spectroscopy (CAMRIS). Additional MRI resources, such as a mock scanner, may be accessed from the Center for Functional Neuroimaging (CfN).

## **Characteristics of the Study Population**

#### **Target population**

38 healthy control participants to collect useable data from 28 healthy participants.

#### **Subjects enrolled by Penn Researchers**

38

#### **Subjects enrolled by Collaborating Researchers**

0

#### **Accrual**

All recruitment will be conducted through the University of Pennsylvania and the surrounding community to find a total of 38 healthy participants. It is assumed that there will be some participants who screen fail, are lost to follow up, withdraw, or complete without usable scanner data. Therefore, we estimate that we will need to consent/enroll up to 38 participants overall, in order to adequately test the hypotheses on at least 28 participants.

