### **Design**

This study will recruit 38 healthy participants, who will be recruited through the community via study advertisements. Prior to any study visits, all subjects will be pre-screened through a phone interview with a trained member of the study team or an online self-report screening, both through REDCap. The study involves 11 study visits. The first study visit will consist of a consenting and extended screening visit. All participants will have the opportunity to ask questions before signing the electronic consent form. We will complete a semi-structured clinical interview and will demonstrate TMS to ensure the participant is comfortable with all study procedures. This visit will be completed both remote and in- person. The second study visit will involve a 1-hour MRI scan. During the scan, the participant will complete multiple computerized tasks. The MRI scan will include both structural and functional scans, and those scans will be used to localize the stimulation target for the subsequent sessions. The third study visit will be a 2-hour TMS/fMRI session, and the participant will engage in behavioral tasks while interleaved rTMS rounds are delivered at different excitatory frequencies (frequency range: 2Hz-20Hz). This scan will be used to determine the optimal stimulation frequency for the individual participant. The fourth, fifth, and sixth study visits will involve neuromodulation with either the optimized frequency or the frequency least successful in moving a participants brain state, as determined from the third study visit. Each subject will receive ~3000 pulses in each session, including the pulses from the motor threshold determination. We will determine the adjusted MT by using the Stokes equation, which accounts for differences in cortical distance from the site relative to motor cortex (where the motor threshold is found). The stimulation amplitude will be equivalent to 110% of the adjusted MT. Prior studies have safely utilized TMS with such design (VanDerwerker et al., 2018; Cristancho, Trapp, Siddiqi, Dixon, & Lenze, 2018). The seventh study visit will involve a 1-hour TMS/fMRI session while the participant is engaging in a behavioral task.. This visit is designed to examine brain and behavioral changes after the first round of neuromodulation. The seventh and the eighth visit will be scheduled at least one week apart. The eighth, ninth, and tenth study visits will mirror the fourth, fifth, and sixth study visits and will involve neuromodulation with either the optimized or least-optimized individual frequency. The order of optimized and least-optimized frequencies will be counterbalanced across participants between Visit 4-6 and Visit 8-10 (i.e., half of the participants will receive stimulations of the two frequencies in one order, and the other half will receive stimulations of the two frequencies in the reverse order). The

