## Procedures

All participants will be recruited through the University of Pennsylvania and the surrounding community. Subjects will be pre-screened for eligibility through phone or online self-report screener in REDCap. Eligible subjects will be invited in for a screening visit. Visit 1 will be a consent/ screening session. This visit will involve remote and in-person procedures. During the remote visit, a coordinator will discuss the Informed Consent Form with the participant. After going through the ICF, participants will be asked to electronically sign at the end of the ICF and complete a Remote ICF Attestation form to ensure they understood all the procedures and risk associated with the study. If they agree to participate, they will complete questionnaires related to their medical history, demographics, and eligibility to receive MRI scans and TMS. After completing the questionnaires, participants will undergo a clinical interview. This interview could be done in person or remote. If participants meet eligibility for these initial procedures, we will schedule an in-person meeting to test TMS. For the TMS demo, participants will receive several short rounds of TMS test pulses to the prefrontal cortex to ensure comfort. During this demonstration we will identify the participants resting motor threshold (MT). MT is defined as the minimum magnetic flux needed to elicit a response in a target muscle in 5 out of 10 trials. MT is the standard in the field for measuring cortical excitability and to reduce seizure risk. While TMS is usually quite tolerable, a minority of participants (20%) cannot tolerate stimulation procedures. Screening data will be recorded in REDCap; this data will be retained indefinitely until the study enrollment is completed. The information collected in this initial visit will determine if the subject meets all inclusion criteria. If participants screen-fail or withdraw, we will assign the clinical interview compensation to their virtual Greenphire Clincard. Upon meeting all criteria for inclusion in the study, subjects will then return to complete a 1-hour baseline MRI scan at Visit 2. All MRI imaging protocols will be reviewed and approved by CAMRIS. An experienced technician and a member of the study team will be present during the MR session to ensure participant safety and well-being. If the participant complains of feeling claustrophobic and does not wish to complete the MRI, the study will be terminated. Emergency personnel and equipment are immediately available to the MRI room should the need arise. It is possible that during the course of the research study, the research staff may notice unexpected findings on an MRI scan. Should this occur, the findings will be assessed by a trained radiologist. The study doctor will inform research subjects of any significant findings. Visit 3 will include fMRI and interleaved TMS/fMRI. During this scan, the participant will perform a working memory N-back task several times. Brain data from the baseline MRI scan (stimulation target in individualized brain space) will be calibrated with the skin and scalp using a Polaris Vicra camera (Brainsight neuronavigation) to allow marking of the stimulation site on a swim cap for the TMS/fMRI session. During the MRI scan, participants will receive interleaved TMS/fMRI probes to the brain targets. The purpose of this TMS/fMRI scan is to probe and modulate and measure activity in targeted neural circuits following our established methods (Chen et al., 2013). Moreover, by building brain decoding models using LSTM RNNs deep-learning technique, we can establish a closed loop of rTMS and brain readouts. As a result, we will be able to fine-tune the rTMS frequency to achieve optimal brain state and maximized working memory performance during this session. Our MRI-compatible TMS system (MagPro X100 Stimulator, MRI-B91 TMS coil) is housed in Stellar Chance (SC3T) and the Hospital of the University of Pennsylvania (HUP 6) at the 3-Tesla MRI machine. The apparatus was installed under the supervision of [name]. a member of CAMRIS. TMS in an MRI scanner involves no additional risks to the subject. Visits 4-6 will involve excitatory rTMS delivered in the

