## Consent

### 1. Consent Process

#### Overview

Consent will be obtained by a member of our research team. Because this study does not involve treatment, coercion is not a concern. Consent will be obtained remotely (via RedCap) where study staff members will discuss the Informed Consent Form, including the purpose of study, procedures, risks, and benefits. They will explain that participating is completely voluntary and that not participating will not change access to treatment in any way. The potential participant will be given the option to consider study enrollment and will not be forced to make a decision the same day. At the end of the ICF, there will be a HIPAA-compliant eSignature field following OCR- RedCap guidelines. By electronically signing the ICF they will be consenting to participate in the study. Enrolled participants will be asked to complete the Remote ICF Attestation Form to ensure they understood all the procedures and risks associated with the study. After the ICF process, we will begin the screening procedures. If the participant meets initial eligibility, they will be invited to an in-person meeting where we will provide a paper copy of the ICF on request. The patient will be reminded before and after enrolling, and before any research procedure that their participation is optional and has no impact on the care they can expect.

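### Does the protocol's own 20% TMS-intolerance figure mean that 38 consented participants cannot yield 28 usable ones?

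*Combined protocol and SAP*

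**What the plan says.** The Accrual section says the team will "need to consent/enroll up to 38 participants overall, in order to adequately test the hypotheses on at least 28 participants". The Target population section gives the same pair of numbers: "38 healthy control participants to collect useable data from 28 healthy participants". As the reason for the difference, Accrual expects that "there will be some participants who screen fail, are lost to follow up, withdraw, or complete without usable scanner data". It gives no rate for any of these losses and no derivation of 38.

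The Procedures section, describing Visit 1, says that "a minority of participants (20%) cannot tolerate stimulation procedures". The order of events matters here. The consent Overview says: "After the ICF process, we will begin the screening procedures". Procedures then says: "If participants meet eligibility for these initial procedures, we will schedule an in-person meeting to test TMS". Tolerance is therefore found out after consent, within the 38.

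On the length of participation, the Design section says: "The study involves 11 study visits". These include a baseline MRI (Visit 2) and three TMS/fMRI sessions (Visits 3, 7 and 11).

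**The concern.** The protocol never puts its two figures together. If one in five consented participants cannot tolerate stimulation, about three quarters of the 10-person allowance is gone by the end of Visit 1. What is left must cover other exclusions at interview or for MRI, people who stop because of claustrophobia, withdrawal over the later visits, and scans that cannot be used. Accrual itself expects some of these losses.

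The usable number matters because Accrual ties 28 to an adequate test of the hypotheses. The main analysis is a within-subject comparison of two stimulation conditions. A participant lost before Visit 11 has no post-stimulation scan for the second condition and drops out of a complete-case paired contrast. A final number in the low twenties would leave the comparison less sensitive than one with 28.

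**Working it through.** **Inputs.** 38 consented and 28 usable (Accrual, Target population); 20% intolerance (Procedures). All other loss rates below are assumptions, because the document gives none.

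**Step 1: the plan's own figure.** The allowance is 38 − 28 = 10, and 10/38 = 26.3%. Inflating 28 for loss d gives 28/(1 − d). With d = 0.25 this is 37.3, rounded up to 38. With d = 0.20 it is 35. So 38 would follow from a total loss of about 25% to 26%, but no total is stated. It is more than the 20% alone requires.

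**Step 2: the 20% alone.** 38 × 0.20 = 7.6 lost and 38 × 0.80 = 30.4 left. The margin over 28 is 2.4. Treating participants as independent, P(at least 28 of 38) with success probability 0.80 is 0.88 (exact binomial).

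**Step 3: break-even for the other losses.** 1 − 28/30.4 = 7.9% combined. Spread equally over three further steps, this is 1 − (28/30.4)^(1/3) = 2.7% each.

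**Step 4: range of assumed other losses.** Expected usable = 38 × 0.80 × (1 − other loss). The last column is 28/[0.80 × (1 − other loss)], rounded up.

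| Other loss (assumed) | Expected usable | P(at least 28) | Consents needed for 28 expected |
|---|---|---|---|
| 0% | 30.4 | 0.88 | 35 |
| 5% combined | 28.9 | 0.71 | 37 |
| 10% combined | 27.4 | 0.49 | 39 |
| 15% combined | 25.8 | 0.29 | 42 |
| 20% combined | 24.3 | 0.14 | 44 |
| 5% at each of three steps | 26.1 | 0.31 | 41 |
| 10% at each of three steps | 22.2 | 0.04 | 49 |

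**Step 5: sensitivity to the 20%.** If intolerance in this sample were 15%, then 38 × 0.85 = 32.3 remain and the break-even is 1 − 28/32.3 = 13.3%. At 10%, 34.2 remain and the break-even is 18.1%.

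**Step 6: what a shortfall would cost.** For a paired t-test at two-sided 5% and 80% power, the smallest detectable standardised effect is 0.55 with 28 participants, 0.58 with 25 and 0.63 with 22. For an effect of 0.55, power falls from 80% at 28 to 69% at 22. These values are illustrative: the protocol states no effect size, power or significance level for 28, so there is no planned detectable effect to correct.

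**The case for a change.** The strongest case for a change is that Accrual itself expects the other losses, so the zero-loss row is not realistic. Even in that row the chance of missing 28 is 1 − 0.88 = 12%. The wording sets 38 as a ceiling, with no stated provision for replacing lost participants. For a study of this length, combined other losses above 7.9% are easy to imagine.

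That much stands: the margin is narrow, and the document does not show how it was chosen. A demonstrated shortfall does not stand. Every row of the table that falls below 28 depends on a rate that the protocol does not contain.

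Several features also work against the pessimistic rows. Phone or online pre-screening comes before consent, so some ineligible people never enter the count of 38. Past participants of the centre may be recruited, and people in several centre studies may not need to repeat screening or the baseline MRI. Intolerant participants would themselves be recorded as screen failures or withdrawals, which Accrual already lists, so applying full separate rates on top of the 20% may count some losses twice. The 20% is also worded as a general statement about TMS, not as a forecast for this sample. The document quantifies none of these effects, so they do not prove that 38 is enough. They do show why the lower rows cannot be taken as the protocol's own result.

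**Conclusion.** No change is needed. The only stated loss rate gives an expected 30.4 usable participants and a 0.88 chance of at least 28, so the two figures are compatible. A shortfall in the expected number needs other losses above 7.9% combined. It is under one person at 10% and about two at 15% (28 − 25.8 = 2.2). These results assume that the full 20% applies after consent and that losses are independent across participants.

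The possible remedies gain little or cost more than they seem to. Lowering the stated target to somewhere between 22 and 26 would replace an unexplained number with one built on disputable assumptions. Counting the 38 from those who pass the Visit 1 tolerance test would mean consenting 38/0.80 = 47.5, about 48. That is a real increase in enrolment, not an edit of wording. What remains is that the assumed loss at each step is not written down. This is missing detail: supplying it would alter neither the design nor the analysis, and the usable number will be known when the data are analysed.

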#### **Key inclusion criteria**

1) 18-60 years old 2) Right handed 3) No psychiatric history as diagnosed by the SCID-V 4) Normal cognition 5) Capacity to give informed consent and follow study procedures 6) Sufficient command of English language to understand and respond to written as well as verbal instructions

#### **Key exclusion criteria**

1) History of neurological disorder or traumatic brain injury (other than mild) 2) Unable to have an MRI scan, or current or prior medical condition that could interfere with the collection or interpretation of MRI data 3) Unable to receive TMS 4) Implanted devices, such as an aneurysm clip or cardiac pacemaker 5) History of stroke, epilepsy, or brain scarring 6) Recent use of psychoactive medications, as determined by investigators 7) Pregnant, nursing, or trying to become pregnant (self-attestation alone) 8) Color blindness 9) Otherwise determined by investigator to be unfit for study

## Vulnerable Populations

### Children Form

**Pregnant women (if the study procedures may affect the condition of the pregnant woman or fetus) Form**

### Fetuses and/or Neonates Form

### Prisoners Form

### Other

**None of the above populations are included in the research study**

**The following documents are currently attached to this item:**

*There are no documents attached for this item.*

### Populations vulnerable to undue influence or coercion

No subjects, including the economically disadvantaged, employees, and/or students at Penn, will be unduly influenced, encouraged, or coerced into participating in this study. These populations will not be targeted or excluded. If they are encountered and would like to participate, the appropriate measures will be taken in order to allow them the opportunity to provide consent.

### Participant recruitment

Please describe the plan to equitably identify and recruit a diverse group of participants that is reflective of the population under study. If this is a multicenter protocol, the recruitment plan should describe the local (Penn) site's plan. Describe: how potential participants may be identified (review of medical records, Slicer Dicer, DAC reports including referrals from physician offices and clinics); who may approach potential participants; methods to achieve sample diversity and inclusiveness; what information may be presented to or discussed with them; and the context and setting in which recruitment will happen.

All participants will be recruited through the University of Pennsylvania and the surrounding community. Subjects will be recruited through flyers, brochures, online advertising (CNDS website, Facebook, Craigslist, iConnect). All recruitment materials, including but not limited to flyers, brochures, referral letters, online postings, and email templates will be IRB-approved before distribution of any of these materials. Study coordinators may also contact participants from past studies at the CNDS who indicated they would be willing to be contacted about participating future studies at the center. Individuals will express interest by initiating contact with the research staff via phone or email for a phone-screening procedure or by completing an online screening form on REDCap. All subjects meeting basic inclusion criteria will be scheduled for a remote screening visit. In order to facilitate the enrollment of interested subjects in multiple studies, center-wide general pre-screening forms, phone screen and self-report screen will be used. The Center for Neuromodulation in Depression and Stress has numerous studies that all are closely related, in both purpose and eligibility criteria, a general pre-screening (both phone and self-report) has been created. Many participants will be eligible for multiple studies and will be presented with the opportunity to participate in all studies that they are eligible for. An additional benefit of a shared or general pre-screening is that participants who do not qualify for a specific study can be informed of other studies they are eligible for. It will be clearly explained to all individuals that this pre-screening is for multiple studies and that their information will be stored in REDCap (option given to have screening done on paper). Additionally, subjects will be recruited through Penn's Office of Clinical Research iConnect volunteer registry. Volunteers who have consented to be contacted regarding studies of interest will be sorted by relevant diagnoses and invited by study team members to fill out an online survey to determine eligibility.

### Recruitment Materials

Is the research team using any recruitment materials? These may include but are not limited to: phone call scripts, radio/video scripts, flyers/brochures, internet postings, email, letters to potential participants, letters to patient physicians, My Penn Medicine (MPM), other direct messaging, etc. For guidance regarding recruitment materials, please review the IRB's guidance on Participant Recruitment Materials online: <https://irb.upenn.edu/mission-institutional-review-board-irb/guidance>

Yes

**Use of Penn Media & Social Media Services**

Will the recruitment plan propose to use any Penn media services (communications, marketing, etc.) for outreach via social media avenues (examples include: Facebook, Twitter, blogging, texting, etc.) or does the study team plan to directly use social media to recruit for the research?

Yes

Please identify which method(s) of social media you will utilize, the content of the text to be used, and the method(s) for posting this information (i.e., using Penn supported communication services). When proposing the text to utilize, please be aware of any social media limitations (i.e., number of characters allowed in a tweet) and any appropriate confidentiality practices necessary to be compliant with posting research recruitment text. NOTE: Penn Medicine must utilize one of the centralized PM Facebook Pages: ClinicalResearch@Penn Facebook page, Penn Medicine Facebook page, PennCancer Facebook page, All clinical research paid Facebook ads must be listed on Clinical Research @ Penn Facebook page, www.facebook.com/ClinicalTrialsAtPenn. Exceptions to the above must get approval from the Penn Medicine Social Media Committee: [contact].

We will post flyers and place brochures throughout the local community to recruit for this study. In addition, participants will be recruited through advertisements in print (e.g. local newspapers), online media/websites (e.g. craigslist.com, researchmatch.org, Penn Medicine, CNDS website, Facebook, and Google ads), as well as radio or TV ads. All recruitment materials, including but not limited to flyers, brochures, referral letters, online postings, and email templates will be IRB-approved before distribution of any of these materials.

